## **8 Adverse Event Reporting**

### **8.1 Adverse Events**

All observed or volunteered AEs regardless of treatment group or suspected causal relationship to the investigational product(s) will be reported as described in the following sections.

### **8.2 Reporting Period**

For SAEs, the active reporting period to the principal investigator begins from the time that the patient provides informed consent, which is obtained prior to the patient's participation in the study, through the completion of cycle 1.

AEs (serious and non-serious) should be recorded on the CRF from the time the patient has taken at least one dose of ribociclib through the last patient visit.

Death must be reported if it occurs during the SAE reporting period after the last dose of ribociclib, irrespective of any intervening treatment.

### **8.3 Definition of Adverse Events**

An AE is any untoward medical occurrence in a clinical investigation patient administered a product or medical device; the event need not necessarily have a causal relationship with the treatment or usage. Examples of AEs include but are not limited to:

- Abnormal test findings
- Clinically significant symptoms and signs
- Changes in physical examination findings
- Hypersensitivity
- Drug abuse
- Drug dependency

Additionally, they may include the signs and symptoms resulting from:

- Drug overdose
- Drug withdrawal
- Drug misuse
- Drug interactions
- Medication error
- Occupation exposure
- Worsening of signs and symptoms of the malignancy under study should be reported as AEs in the appropriate section in the CRF

Disease progression assessed by measurement of malignant lesions on radiographs or other methods should not be reported as AEs.

### **8.3.1 Medication Errors**

Medication errors may result from the administration or consumption of the wrong drug, by the wrong patient, at the wrong time, or at the wrong dosage strength.

Such medication errors occurring to a study participant are to be captured on the medication error CRF which is a specific version of the AE page, and on the SAE form when appropriate.

Medication errors are reportable irrespective of the presence of an associated AE/SAE, including:

- Medication errors involving patient exposure to the investigational product
- Potential medication errors or uses outside of what is foreseen in the protocol that does or does not involve the participating patient.

Whether or not the medication error is accompanied by an AE, as determined by the investigator, the medication error should be captured on the medication error version of the AE page and, if applicable, any associated AE(s) are captured on an AE CRF page.

## **8.4 Abnormal Test Findings**

The criteria for determining whether an abnormal objective test finding should be reported as an AE are as follows:

- Test result is associated with accompanying symptoms; and/or
- Test result requires additional diagnostic testing or medical/surgical intervention; and/or

- Test result leads to a change in study dosing (outside of protocol-stipulated dose adjustments) or discontinuation from the study, significant additional concomitant drug treatment, or other therapy; and/or
- Test result is considered to be an AE by the investigator.

Merely repeating an abnormal test, in the absence of any of the above conditions, does not constitute an AE. Any abnormal test result that is determined to be an error does not require reporting as an AE.

## 8.5 Serious Adverse Events

An SAE is any untoward medical occurrence at any dose that:

- Results in death
- Is life-threatening (immediate risk of death)
- Requires inpatient hospitalization or prolongation of existing hospitalization
- Results in persistent or significant disability/incapacity (substantial disruption of the ability to conduct normal life functions);
- Results in congenital anomaly/birth defect

Progression of the malignancy under study (including signs and symptoms of progression) should not be reported as an SAE unless the outcome is fatal within the safety reporting period. Hospitalization due to signs and symptoms of disease progression should not be reported as an SAE. If the malignancy has a fatal outcome during the study or within the safety reporting period, then the event leading to death must be recorded as an AE and as an SAE with CTC Grade 5 (see Section on Severity Assessment).

Medical and scientific judgment is exercised in determining whether an event is an important medical event. An important medical event may not be immediately life-threatening and/or result in death or hospitalization. However, if it is determined that the event may jeopardize the patient or may require intervention to prevent one of the other AE outcomes, the important medical event should be reported as serious. Examples of such events are intensive treatment in an emergency room or at home for allergic bronchospasm; blood dyscrasias or convulsions that do not result in hospitalization; or development of drug dependency or drug abuse.

If an AE meets any of the following criteria, it is to be reported to the DSMC as an SAE:

- 1) **Death of Patient** An event that results in the death of a patient.
- 2) **Life-Threatening** An event that, in the opinion of the Investigator, would have resulted in immediate fatality if the medical intervention had not been taken. This does not include an event that would have been fatal if it had occurred in a more severe form.

- 3) **Hospitalization** (unless planned for observation, protocol compliance, elective procedures, social reasons) **or**
- 4) **Prolongation of Hospitalization** An event that results in an admission to the hospital for any length of time or prolongs the patient's hospital stay. This does not include an emergency room visit or admission to an outpatient facility.
- 5) **Congenital Anomaly** An anomaly detected at or after birth, or any anomaly that results in fetal loss.
- 6) **Persistent or Significant Disability/Incapacity** An event that results in a condition that substantially interferes with the activities of daily living of a study patient. Disability is not intended to include experiences of relatively minor medical significance such as headache, nausea, vomiting, diarrhea, influenza, and accidental trauma (e.g., sprained ankle).
- 7) **Important Medical Event Requiring Medical or Surgical Intervention to Prevent Serious Outcome** An important medical event that may not be immediately life-threatening or result in death or hospitalization, but based on medical judgment may jeopardize the patient and may require medical or surgical intervention to prevent any of the outcomes listed above (i.e., death of patient, life-threatening, hospitalization, prolongation of hospitalization, congenital anomaly, or persistent or significant disability/incapacity). Examples of such events include allergic bronchospasm requiring intensive treatment in an emergency room or at home, blood dyscrasias or convulsions that do not result in inpatient hospitalization, or the development of drug dependency or drug abuse.

Dose-limiting toxicities are defined as AEs that are possibly, probably, or definitely related to the therapy (any part of the combination) and would require treatment discontinuation.

## 8.6 Hospitalization

Hospitalization is defined as any initial admission (even less than 24 hours) in a hospital or equivalent healthcare facility or any prolongation to an existing admission. Admission also includes transfer within the hospital to an acute/intensive care unit (e.g., from the psychiatric wing to a medical floor, medical floor to a coronary care unit, or neurological floor to a tuberculosis unit). An emergency room visit does not necessarily constitute a hospitalization; however, the event leading to the emergency room visit should be assessed for medical importance.

Hospitalization does not include the following:

- Rehabilitation facilities
- Hospice facilities
- Respite care (i.e. caregiver relieve)
- Skilled nursing facilities
- Nursing homes
- Same-day surgeries

Hospitalization or prolongation of hospitalization in the absence of a precipitating, clinical AE is not an SAE. Examples include:

- Admission for treatment of a preexisting condition not associated with the development of a new AE or with a worsening of the preexisting condition (e.g., for work-up of persistent pre-treatment lab abnormality);
- Social admission (e.g., patient has no place to sleep);
- Administrative admission (e.g., for yearly physical examination);
- Protocol-specified admission during a study (e.g., for a procedure required by the study protocol);
- Optional admission not associated with a precipitating clinical AE (e.g., for elective cosmetic surgery);
- Hospitalization for observation without a medical AE;
- Pre-planned treatments or surgical procedures. These should be noted in the baseline documentation for the entire protocol and/or for the individual patient;
- Admission exclusively for the administration of blood products

Diagnostic and therapeutic non-invasive and invasive procedures, such as surgery, should not be reported as AEs. However, the medical condition for which the procedure was performed should be reported if it meets the definition of an AE. For example, an acute appendicitis that begins during the AE reporting period should be reported as the AE, and the resulting appendectomy should be recorded as treatment of the AE.

## 8.7 Severity Assessment

AEs will be graded according to the National Cancer Institute Common Terminology Criteria (NCI CTC), (Version 5.0). Note the distinction between the severity and the seriousness of an AE. A severe event is not necessarily an SAE. For example, a headache may be severe (interferes significantly with the patient's usual function) but would not be classified as serious unless it met one of the criteria for SAEs, listed above.

The study Investigator will rate the severity of each AE according to the NCI CTCAE Version 5.0. For AEs not captured by the NCI CTCAE Version 5.0, the following should be used:

- 1) **Grade 1 (Mild)** The AE is transient and easily tolerated by the patient. No dose adjustment recommended.
- 2) **Grade 2 (Moderate)** The AE causes the patient discomfort and interrupts the patient's usual activities. Interrupt therapy until grade <1, reinitiate ribociclib at the same dose, if AE reoccurs at grade 2, hold until grade <1, and restart at the next lower dose level.
- 3) **Grade 3 (Severe):** The AE causes considerable interference with the patient's usual activities. Interrupt therapy until grade <1, reinitiate ribociclib at the same dose, if AE reoccurs at grade 2, hold until grade <1, and restart at the next lower dose level. If toxicity reoccurs grade 3 discontinue permanently.

- 4) **Grade 4 (Life Threatening)** The AE causes considerable interference with the patient's usual activities and maybe incapacitating or life-threatening. Discontinue ribociclib.
- 5) **Grade 5 (Severe, Resulting in Death)** The AE resulted in the death of the patient.

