Grade 4: Life-threatening consequences; urgent intervention indicated	Discontinue ribociclib.

Table 12: Dose Modification and Management for Other Toxicities that are deemed  
related and clinically significant by the treating physician\*

Grade 1 or 2	Grade 3	Grade 4
--------------	---------	---------

No dose adjustment is required. Initiate appropriate medical therapy and monitor as clinically indicated	Dose interruption until recovery to Grade $\leq 1$ then resume ribociclib at same dose level. If Grade 3 recurs, resume ribociclib at the next lower dose level.	Discontinue ribociclib.
--	---	-------------------------

\*Excluding adverse reactions discussed in tables 5-11.

Table 13. Dose Modifications for Toxicities Related to Ribociclib

Starting dose	600 mg
First dose reduction	400 mg
Second dose reduction	200 mg

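### For related, clinically significant AEs that CTCAE v5.0 does not capture, Section 8.7 and Table 12 give different dosing orders for Grade 2 and for recurrent Grade 3

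*Combined protocol and SAP*

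**What the plan says.** Section 8.7 (Severity Assessment) grades events by CTCAE v5.0 and then adds a fallback list: "For AEs not captured by the NCI CTCAE Version 5.0, the following should be used". The list goes beyond severity definitions, because Grades 1 to 4 each carry a dosing order. At Grade 2: "The AE causes the patient discomfort and interrupts the patient's usual activities. Interrupt therapy until grade <1, reinitiate ribociclib at the same dose". The Grade 3 entry begins with the same hold and same-dose restart, and continues: "if AE reoccurs at grade 2, hold until grade <1, and restart at the next lower dose level. If toxicity reoccurs grade 3 discontinue permanently". The list does not require the event to be related to ribociclib.

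Table 12 in Section 5.4 (Dose Modifications) covers other toxicities that are deemed "related and clinically significant by the treating physician". Its footnote sets one limit: "Excluding adverse reactions discussed in tables 5-11". For Grade 1 or 2 the order is: "No dose adjustment is required. Initiate appropriate medical therapy and monitor as clinically indicated". For Grade 3 the dose is interrupted until recovery to Grade 1 or lower, "then resume ribociclib at same dose level. If Grade 3 recurs, resume ribociclib at the next lower dose level". Table 13 gives the steps: a 600 mg start, 400 mg as the "First dose reduction", then 200 mg.

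Three general bullets in Section 5.4 also bear on this. Grading follows CTCAE v5.0, treatment is delayed until a toxicity resolves to Grade 1 or lower, and it may restart at that level. The last two allow return to baseline where the patient was at Grade 2 on entry.

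**The concern.** The two scopes overlap. An event that CTCAE does not capture, that the treating physician judges related and clinically significant, and that lies outside Tables 5-11 meets the condition for the Section 8.7 list and also the condition for Table 12. Neither place mentions the other.

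These are operative dosing and stopping rules in a multicentre study. A clinician who opens the dose-modification section reaches Table 12 and finds no pointer to Section 8.7. One who grades the event under Section 8.7 finds a dosing order there and has no reason to look further. Two sites could each follow the text and treat the same event differently, at the extreme with a permanent stop at one and 400 mg at the other. The label could differ as well. Section 8.5 defines a dose-limiting toxicity as a related event that would require treatment discontinuation, which a related recurrent Grade 3 event would do under Section 8.7 but not under Table 12.

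**Working it through.** No sample size, rate or power figure is involved, so the check is a side-by-side reading. Take a patient on the 600 mg starting dose with an event in the overlap, and apply the steps in Table 13.

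| Event | Section 8.7 | Table 12 | Comparison |
|---|---|---|---|
| Grade 1 | 600 mg continued | 600 mg continued | Agree |
| Grade 2, first | Hold, then 600 mg | 600 mg continued | Differ (point 1) |
| Grade 2, recurring after Grade 2 | Hold, then 400 mg | 600 mg continued | Differ (point 1) |
| Grade 2, recurring after Grade 3 | Hold, then 400 mg | 600 mg continued | Differ (point 1) |
| Grade 3, first | Hold, then 600 mg | Hold, then 600 mg | Agree, apart from the restart threshold |
| Grade 3, recurring after Grade 3 | Permanent stop | Hold, then 400 mg | Differ (point 2) |
| Grade 4 | Permanent stop | Permanent stop | Agree |

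The three Grade 2 rows are one disagreement: whether a Grade 2 event triggers a hold at all. Recurrent Grade 3 is the second. That makes two substantive points.

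The restart threshold is a separate matter. Section 8.7 asks for recovery to below Grade 1, which read literally means complete resolution. Table 12 and the general restart bullet in Section 5.4 ask for Grade 1 or lower. A patient whose Grade 3 event has settled at Grade 1 stays on hold under Section 8.7 and restarts at 600 mg under Table 12. Two things suggest caution. The document shows signs of unreliable inequality symbols: the CYP3A5 screening window is under 28 days in the document history but at most 28 days in the Table 14 footnote, and Table 11 has reversed signs at Grades 1 and 4 for platelets. Against that, the below-Grade-1 wording appears four times in Section 8.7. It may be a slip, so it is not counted here, and neither point above depends on it.

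Is the overlap empty? By the protocol's own account, perhaps not. The adverse event log in Appendix 14.6 lists hot flush, marks it as having no CTCAE entry, and describes its Grade 2 as limiting daily activities. If such an event were judged related and clinically significant, Section 8.7 would hold ribociclib and Table 12 would continue it. Whether CTCAE v5.0 really omits hot flush cannot be checked from the documents.

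**The case against.** The strongest reply is that the text already points to an answer. Section 8.7 gives an express instruction for exactly this class, and Section 5.4 says that its grading is by CTCAE v5.0. Table 12 is entered by grade, and an event without a CTCAE grade gets one only from Section 8.7, where the dosing order sits beside it. On the usual rule that the specific provision displaces the general one, Section 8.7 governs these events and Table 12 the rest. The general bullet on delaying treatment also leans towards a Grade 2 hold.

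Much of this stands. A reader might infer that the documents are silent on which rule applies, and that would go too far, because there is a reasonable reading in favour of Section 8.7. It remains an inference. The sentence in Section 8.7 introduces a severity scale and does not mention Table 12, and Table 12 lists its exclusions without listing this class. The general bullets do not settle the matter either: their restart threshold matches Table 12 rather than Section 8.7, and they say nothing about Grade 3 recurrence.

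The second reply is that the case hardly arises. Ribociclib is given for 21 days and patients are followed for one 28-day cycle, after which treatment follows standard of care. A permanent stop against 400 mg needs a Grade 3 event, recovery, restart and a second Grade 3 event within that time. Hot flush is not among the ribociclib events listed in Section 1.2.4, while Table 12 requires relatedness. This stands in full and limits the size of the point.

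**Conclusion.** For adverse events that CTCAE v5.0 does not capture, that are deemed related and clinically significant, and that lie outside Tables 5-11, the two sets of orders conflict on two substantive points: handling of Grade 2, and recurrent Grade 3. The restart threshold also differs and may be a slip. This is a drafting inconsistency that calls for a minor protocol correction.

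Two stronger readings are tempting, and the documents do not support them. A reader might count four or five separate conflicts by listing first and recurring Grade 2 events apart and adding the threshold. The Grade 2 rows are one disagreement and the threshold is uncertain. A reader might also infer harm to the primary endpoint, since a hold before the day 8-16 sampling visit could lower the measured AUC. The documents give no frequency for such holds and no basis for a magnitude, so no effect on AUC is claimed.

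The conclusion assumes that the Section 8.7 dosing sentences are meant to be followed, as their wording indicates, and that at least some events fall in the overlap. The number of patients cannot be derived and is probably small.

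**What to change.** Make one rule govern. The choice is the sponsor's.

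- **Option A, if Table 12 is intended:** keep the severity definitions in Section 8.7, delete its dosing orders, and refer to Section 5.4 and Table 12. The cross-reference should name Table 12, because the general delay bullet in Section 5.4 does not say at which grade a hold begins.
- **Option B, if the stricter orders are intended:** extend the Table 12 exclusion footnote with *and AEs not captured by CTCAE v5.0 (see Section 8.7)*, and change the restart threshold in Section 8.7 to Grade 1 or lower so that it matches Section 5.4.

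Option A costs a few deleted sentences and one cross-reference. Option B costs one clause and one corrected threshold. Neither changes visits, sample size or analysis.

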## 8.8 Causality Assessment

The investigator's assessment of causality must be provided for all AEs (serious and non-serious); the investigator must record the causal relationship in the CRF, as appropriate, and report such an assessment in accordance with the serious adverse reporting requirements if applicable. An investigator's causality assessment is the determination of whether there exists a reasonable possibility that the investigational product caused or contributed to an AE; generally, the facts (evidence) or arguments to suggest a causal relationship should be provided. If the investigator does not know whether or not the investigational product caused the event, then the event will be handled as "related to investigational product" If the investigator's causality assessment is "unknown but not related to investigational product", this should be clearly documented on study records.

In addition, if the investigator determines an SAE is associated with study procedures, the investigator must record this causal relationship in the source documents and CRF, as appropriate, and report such an assessment in accordance with the SAE reporting requirements, if applicable.

## 8.9 Withdrawal Due to Adverse Events

Withdrawal due to AE should be distinguished from withdrawal due to other causes, according to the definition of AE noted earlier, and recorded on the appropriate AE CRF page. When a patient withdraws because of an SAE, the SAE must be reported in accordance with the reporting requirements defined below.

## 8.10 Eliciting Adverse Event Information

The investigator is to report all directly observed AEs and all AEs spontaneously reported by the patient. In addition, each study patient will be questioned about AEs.

## 8.11 Reporting Requirements

### 8.11.1 Serious Adverse Events

In the event of an SAE, whether related to study drugs, study procedures or even if not directly related to any study intervention, the study team will notify the Principal

Investigator and Co-Principal Investigators, via email and cc: [[contact]](mailto:[contact]) within 24 hours of being made aware of the SAE. SAEs should be reported on the FDA Medwatch form.

SAEs should be reported to the IRB, per local IRB guidelines, and to the DSMC, per DSMC reporting guidelines.

### **8.11.2 Non-Serious Adverse Events**

All AEs will be reported on the AE page(s) of the CRF. It should be noted that the form for the collection of SAE information is not the same as the AE CRF. Where the same data are collected, the forms must be completed in a consistent manner. For example, the same AE term should be used in both forms. AEs should be reported using concise medical terminology on the CRFs as well as on the form for the collection of SAE information.

## **9 Data Analysis and Statistical Methods**

### **9.1 Sample Size, Accrual and, Study Duration**

This study is powered to assess the primary outcome (ribociclib in CYP3A5 poor metabolizers vs. CYP3A5 intermediate or normal metabolizers) independently within each race-based cohort. The pharmacokinetic study used to inform the FDA's decision to suggest alternative dosing for patients prescribed a strong CYP3A inhibitor (ritonavir) exhibited a 3.2-fold increase in AUC (15). Genotype may have a lower effect, but the extent of the effect is unclear. We will aim to detect a minimum clinically meaningful change: 2-fold change in AUC, which is less than the fold changes seen in the ritonavir CYP3A drug interaction pharmacokinetic study. In the meantime, data from the same pharmacokinetic study showed the standard deviation of AUC fold change (in  $\log_2$  scale) was 0.56. Given that the groups in our study are considered similar, to be conservative, we used the standard deviation of 0.75 in our calculation.

Allelic frequencies for CYP3A5 are provided from CPIC and PharmGKB and translated to phenotypes via the Hardy-Weinberg equation (32). Based on these frequencies (normal metabolism: 35%; intermediate metabolism: 48%; poor metabolism: 16%), a sample size of 18 would provide 80% power at an  $\alpha=0.05$  to detect a 2-fold change in AUC between CYP3A5 poor metabolizers vs. CYP3A5 expressors (i.e., CYP3A5 intermediate or normal metabolism) in African Americans/Blacks. Based on the allelic frequencies for Non-Hispanic Whites (normal metabolism: 0.6%; intermediate metabolism: 14.7%; poor metabolism: 84.6%), a sample size of 18 would also provide 80% power at an  $\alpha=0.05$  to detect a 2-fold change in AUC between CYP3A5 poor metabolizers vs. CYP3A5 expressors (i.e., CYP3A5 intermediate or normal metabolism).

Thus, an overall sample size of 36 would provide adequate power to independently test the primary outcome in the two race-based cohorts.

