Study Design	
This prospective, multicenter, cohort study will assess ribociclib (600 mg PO daily) pharmacokinetics and pharmacogenomics in female patients with HR+/HER2- metastatic breast cancer. This design will be used for two independent, race-based cohorts: 18 African American/Black patients and 18 Non-Hispanic White patients. Women are eligible if they are older than 18, have HR+/HER2- mBC and are candidates for treatment with a CDK 4/6 inhibitor and endocrine therapy. Patients are ineligible if currently prescribed a medication that inhibits or induces the CYP3A isoenzymes, have baseline electrocardiogram abnormalities, or are otherwise considered to be ineligible for ribociclib. Participants will provide serial blood samples during the first cycle. Plasma samples will be analyzed via mass spectrometry to characterize the pharmacokinetics (e.g., <math>AUC_{0-24}</math>, <math>C_{max}</math>). Pharmacogenetic testing will be performed using the PharmacogenoScan™ microarray, which tests 4,627 markers in 1,191 genes, including variants in CYP3A4 and CYP3A5.
 
The primary outcome is powered to detect a minimum clinically meaningful change, a 2-fold change in <math>AUC</math>, which is less than the 3.2-fold change seen in the mentioned CYP3A drug interaction pharmacokinetic study. Based on CYP3A5 allelic frequencies, a sample size of 36 will provide 80% power to independently test the primary outcome in the two race-based cohorts.

Multi-Institutional Trial Management	
Personnel
 
At each site, personnel dedicated to this protocol will be:
 
 
- A study PI
 
- A research coordinator
 
- A data manager
 

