## **3.3 Inclusion Criteria**

Patients must meet all the following inclusion criteria to be eligible for enrollment in the study:

- Signed informed consent must be obtained prior to any screening procedures that are not standard of care.
- Female  $\geq 18$  years old at the time of informed consent.
- Those who self-identify as African American or Black are eligible for that respective cohort
- Those who self-identify as non-Hispanic White are eligible for that respective cohort
- Postmenopausal or premenopausal. Patient has a known menopausal status at the time of the informed consent form signature. The patient is considered postmenopausal if: i) she has had prior bilateral oophorectomy; ii) is age  $\geq 60$  years; iii) is age  $<60$  years and has had amenorrhea for 12 or more months (in the absence of chemotherapy, tamoxifen, toremifene, or ovarian suppression) and follicle-stimulating hormone (FSH) and estradiol in the postmenopausal range per local normal ranges. All other patients who do not meet the criteria for postmenopausal status are considered premenopausal and will receive a luteinizing hormone-releasing hormone (LHRH) agonist (i.e., goserelin, leuprolide) for ovarian suppression
- Each race-based cohort has a predetermined number of patients with each CYP3A5 phenotype per the sample size calculation (section 9.1). Patients will be screen for CYP3A5 according to section 3.6.1.

- African American or Black
  - At least 3 participants who are CYP3A5 poor metabolizers
  - No more than 15 participants who are CYP3A5 intermediate or normal metabolizers
- Non-Hispanic White
  - At least 3 participants who are CYP3A5 intermediate or normal metabolizers
  - No more than 15 participants who are CYP3A5 poor metabolizers
- Patient has advanced (loco-regionally recurrent or metastatic) breast cancer not amenable to curative therapy
- Treated, stable and asymptomatic brain metastases are permitted
- ECOG performance status 0-3
- Documentation of estrogen receptor (ER) positive and/or progesterone receptor (PR) positive tumor ( $\geq 1\%$  positive stained cells) based on most recent tumor biopsy (discuss with the Principal Investigator if results in different biopsies are discordant in terms of hormone receptor positivity) utilizing an assay consistent with local standards.

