## 9.2 Statistical Analysis Plan

Primary analyses will be performed as follows. Within each race-based cohort, the ribociclib exposure which measured by ribociclib AUC will be summarized by median [Interquartile range, IQR], and two-sample t-test if normality holds or Wilcoxon-Mann-Whitney test will be used to compare AUC between CYP3A5 poor metabolizers and CYP3A5 intermediate or normal metabolizer in each independent race-based cohort. Secondary analyses will be performed as follows. Descriptive statistics will be used to characterize the data profile, frequency and percentages for categorical variables, and mean (SD) or median [IQR] for continuous variables based on the data normalization. Multiple regression will be used to identify variables associated with ribociclib AUC. To best account for any factor that may affect ribociclib exposure, covariates to be assessed include CYP3A5 metabolism status, renal function, liver function, age, race, weight, sex, among others. Any covariates with  $P < 0.2$  on univariate analysis will enter the stepwise multiple linear regression model, with  $P < 0.05$  considered statistically significant. This methodology will also be used to assess a change in absolute neutrophil count and QTc as the outcome variable. Depending on data distribution, a two-sample t-test or Wilcoxon-Mann-Whitney test will be used for 1) a change (baseline and C1D8-C1D16) in continuous variables (e.g., QTc, absolute neutrophil count) between CYP3A5 poor metabolizers and CYP3A5 intermediate or normal metabolizers, 2) to check the association between a continuous variables and categorical risk factors. Pearson correlation coefficient or Spearman correlation coefficient will be calculated to measure the association between two continuous variables. Fisher's exact test will be used for checking the association between two categorical variables. AEs will be assessed with descriptive statistics and univariate logistic regression will assess the occurrence of specific AEs with pharmacokinetic properties (e.g., AUC,  $C_{max}$ ). The approach from the linear regressions will be adapted to logistic regression to identify covariates associated with the occurrence of grade III or IV neutropenia.

Descriptive analysis of the PRO-CTCAE adverse event log to determine frequency of adverse events by race and by CYP3A5 genotype.

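### The 80% power stated per cohort does not follow from the inputs in section 9.1: at 3 vs 15 an SD of 0.75 gives about 51%, and about 80% only after an unstated conversion

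*Combined protocol and SAP*

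**What the plan says.** Section 9.1 sets the target: "We will aim to detect a minimum clinically meaningful change: 2-fold change in AUC". On variability, it says that "data from the same pharmacokinetic study showed the standard deviation of AUC fold change" on the log2 scale was 0.56, the study being the ritonavir interaction study. It then says: "Given that the groups in our study are considered similar, to be conservative, we used the standard deviation of 0.75 in our calculation". From these inputs it concludes that "a sample size of 18 would provide 80% power at an" alpha of 0.05 in the African American/Black cohort, says the same of the Non-Hispanic White cohort, and ends that "an overall sample size of 36 would provide adequate power to independently test the primary outcome in the two race-based cohorts". The synopsis repeats that "a sample size of 36 will provide 80% power to independently test the primary outcome in the two race-based cohorts".

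The group sizes come from the phenotype frequencies in 9.1 and the quotas in 3.3. For the African American/Black cohort the quota is "At least 3 participants who are CYP3A5 poor metabolizers" and at most 15 intermediate or normal metabolizers. The Non-Hispanic White cohort mirrors this. Section 3.6.1 presents three minority-phenotype patients per cohort as what the study needs to be powered, and 4.3.7 allows genotype screening to be bypassed once those minimums are met.

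For the analysis, 9.2 says that a "two-sample t-test if normality holds or Wilcoxon-Mann-Whitney test will be used to compare AUC" between phenotypes within each cohort. It does not mention a log transformation or sidedness.

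**The concern.** The comparison in 9.2 is between different patients, so its power depends on the between-patient SD of (log) AUC. The only variability figure with a stated source is the SD of a fold change, which is a contrast between two AUCs. The 0.75 that replaces it carries no label. The two candidate meanings give very different power with 18 patients split about 3 to 15.

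This figure is the only justification given for the cohort size of 18 and for the three-patient minimum. If 0.75 is a between-patient SD, a true 2-fold difference would be missed about half the time in a cohort split 3 vs 15, while the protocol describes that cohort as powered.

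**Working it through.** **Inputs.** From 9.1: difference log2(2) = 1.0; SD 0.75 (source figure 0.56); alpha 0.05; 18 per cohort. Expected minority group: 18 x 0.16 = 2.9 (African American/Black poor metabolizers) and 18 x (0.006 + 0.147) = 2.8 (Non-Hispanic White expressors), so about 3 vs 15, which is also the quota. Assumptions of this review: the t-test is two-sided and run on log2 AUC.

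**Formula.** Noncentrality = 1.0 / (SD x sqrt(1/n1 + 1/n2)). Power comes from the noncentral t distribution with n1 + n2 - 2 = 16 degrees of freedom and critical value 2.120. At 3 vs 15, sqrt(1/3 + 1/15) = 0.632.

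**Trying to reproduce 80% at 3 vs 15 with the SDs named in 9.1**

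| SD entered directly | Noncentrality | Power, two-sided t |
|---|---|---|
| 0.75 | 1/(0.75 x 0.632) = 2.108 | 50.8% |
| 0.56 | 1/(0.56 x 0.632) = 2.823 | 75.5% |

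With SD 0.75, a one-sided t-test gives 64.5%, the two-sided normal approximation 55.9%, and an even 9 vs 9 split 75.7% by t-test. Solving for 80% at 3 vs 15 gives a largest between-patient SD of 0.530.

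**Routes that come near 80%**

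- 0.75/sqrt(2) = 0.530: noncentrality 2.981, power 79.9%. This keeps all the stated inputs but adds a step that 9.1 does not mention.
- SD 0.56 at 3 vs 15 by normal approximation: 80.6%, but this ignores the 0.75.
- SD 0.75 at 9 vs 9 by normal approximation: 80.7%, but this ignores the phenotype split.
- 0.75 x ln 2 at 3 vs 15: 81.5%, but this contradicts the log2 label.

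The sqrt(2) step is the most plausible of these. If a log fold change is the difference of two log AUCs with equal variance s^2 and correlation r, its variance is 2s^2(1 - r), so s = 0.75/sqrt(2(1 - r)). Dividing by sqrt(2) is the case r = 0.

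**Both readings side by side** (averages take the final minority count as max(k, 3) with k ~ Binomial(18, p), p = 0.16 and 0.153; exactly 3 vs 15 then has probability 0.68 and 0.71)

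| | SD 0.75 between patients | SD 0.530 (fold-change SD, r = 0) |
|---|---|---|
| t-test, 3 vs 15 | 50.8% | 79.9% |
| t-test, 4 vs 14 | 59.8% | 87.7% |
| t-test, averaged | about 55% | about 83% |
| Wilcoxon, 3 vs 15 (simulated, log-normal AUC) | about 42% | about 71% |

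With a between-patient SD of 0.75 at 3 vs 15, the difference detectable with 80% power is 1.416 on log2, or 2^1.416 = 2.67-fold.

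**Sensitivity of the conversion at 3 vs 15.** r = 0: SD 0.530, power 79.9%. r = 0.25: SD 0.612, power 67.9%. r = 0.5: SD 0.750, power 50.8%. The documents give no correlation, so these values of r are assumptions.

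**The case against.** The strongest reply is that 0.75 has a natural antecedent. The sentence before it names the SD of a log2 fold change, and the 0.75 reads as that quantity inflated for caution. Converted to a per-patient SD with independent AUCs, it gives 79.9% at exactly the planned split. Because three is a minimum, power under this reading is usually at or above the claim: 87.7% at 4 vs 14 and about 83% averaged. The positive correlations shown above presuppose paired data in the source study, whose design the documents do not describe. The hypothesis in 1.5 is also directional, and a one-sided test at r = 0.25 would give 79.5%.

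Most of this stands. A reader might infer from the 51% that the sample size calculation is wrong. The documents do not support that, because the reading that their wording favours does reproduce 80%. A reader might also infer that a null result could never exclude a 2-fold change. That is too strong: with SD 0.75 and an observed ratio of 1.0, the upper 95% limit is 2.01 at 3 vs 15 but 1.87 at 4 vs 14.

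The reply does not supply the missing step. Section 9.1 states no conversion and does not justify treating the two log AUCs as uncorrelated with a variance equal to the between-patient variance. One-sided testing is not stated, and with SD 0.75 entered directly it reaches only 64.5%. Even at SD 0.530, the Wilcoxon option that 9.2 allows has about 71% power at 3 vs 15.

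**Conclusion.** The stated 80% is not reproduced from its stated inputs. This is not a proven miscalculation. At 3 vs 15, power is 51% if 0.75 is the between-patient SD of log2 AUC. It is 79.9% if 0.75 is a fold-change SD converted under zero correlation, and lower under any positive correlation. The documents do not settle which meaning applies, though their wording leans to the fold-change SD.

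The t-test figures rest on a two-sided test on log2 AUC with equal variances; the Wilcoxon figures rest on log-normal AUC. The point should be fixed because the power claim is the stated basis for the three-patient rule in 3.6.1 and 4.3.7, and the repair is cheap. If the conversion was made and its assumptions can be defended, the 80% can stay for the t-test at 3 vs 15.

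**What to change.** In 9.1 and the synopsis, state the between-patient SD of log2 AUC that was used and how it was obtained, the sidedness and the group sizes. In 9.2, specify that the primary test is on log AUC. Then restate the power or the detectable fold change to match.

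- If 0.75 was converted from a fold-change SD, give the resulting SD and the assumed correlation, and show power over a range (80% at 0, 68% at 0.25, 51% at 0.5, all at 3 vs 15).
- If the between-patient SD is 0.75, state about 51% power for a 2-fold change at 3 vs 15, or about 2.7-fold at 80% power. Remove from 3.6.1 the statement that three minority-phenotype patients make the study powered.

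No patients need to be added. The cost is protocol and SAP wording, and possibly a less favourable stated power.
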